3.2 Clinical Use of FGF-2

A study in 87 subjects with chronic tympanic membrane perforation was recently published. The objectives of the study was to measure the rate of complete closure of chronic TMR using basic fibroblast growth factor (bFGF) combined with an atelocollagen/silicone bilayer membrane patch. The study assessed closure of TMR in 87 subjects using bFGF, which is thought to promote the regeneration of TM tissues by facilitating the growth of fibroblasts and collagen fibers. A dose of 10 mcg of bFGF was administered every 21-days. Study methods included a procedure using an operating microscope. The results of the study reported mean perforation size before treatment of 14.4%. Complete closure of the TMR was achieved in 80 subjects (92.0%), whereas pinholes remained in 5 subjects (5.7%), and small perforations were observed in 2 subjects (2.3%). In the subjects with complete closure, the TMR closed after an average 1.8 treatments, and hearing improved by 13.6 dB. In conclusion the study demonstrated that bFGF combined with atelocollagen is effective for the conservative treatment of TMR (Hakuba et al, 2009).

Kanemaru et al (2011) have reported updated findings from their 2009 presentation involving 63 subjects, in which 53 received tympanic membrane repair using gelatin sponge and fibrin glue with b-FGF and 10 were assigned to the control group of gelatin sponge and fibrin glue alone. The study sought to determine closure rates, hearing level, and sequelae after 3 weeks post treatment. Of the 53 subjects who received b-FGF treatment, 52 had a complete closure of the TMP (98.1%) compared to 1 out of 10 (10%) of the control group subjects. Hearing level improved for all subjects with successful TM repair. No serious sequelae were observed. Some of the perforations were pan tympanic and included loss of nearly all of the tympanic membrane. They concluded that bFGF may be a simple, cost-effective treatment option for subjects with chronic tympanic membrane perforations. Human FGF-2 has been the most studied FGF isoform and its production and clinical applications in wound healing are well described.

Zhang and Lou (2012) present findings on the direct application of b-FGF on TMPs due to direct traumatic penetration. Of the 104 subjects, 51 were assigned to control (spontaneous healing) and 53 were assigned to FGF treatment. Statistically significant findings were observed. After 3 months, of the 93 patients analyzed, there was 100% closure of all TMPs in the experimental group compared to 77% in the control/spontaneous healing group. The treatment

group also had significantly faster closing times compared to the control group, on average 12.6 ± 1.2 days compared to 43.1 ± 2.5 days, respectively.

Lou, Wang & Yu (2014) present some of the most current research on the impact of basic fibroblast growth factor on human tympanic membrane perforations. In their 126-subject study, patients were dosed with either (Group 1) 2-3 drops of bFGF solution daily, approximately 0.1-0.15 mL or (Group 2) 5-6 drops of bFGF solution daily, approximately 0.25-0.3 mL. Follow up occurred at 3 months, at which time closure rate, closure time, and rate of otorrhea between the higher- and lower-dose groups were compared. This study found that, for perforations of the same size, subjects who received the higher dose showed significantly improved purulent otorrhea rate compared with the lower-dose group ($p < 0.01$). Closure rate of the middle-sized perforations did not differ significantly between the two groups ($p > 0.05$). The lower-dose group had a significantly shorter closure time (5 days) compared with the higher-dose group ($p < 0.05$). This study suggests that continued daily application of a lower dose of bFGF has the capacity to 1) shorten the closure time of human traumatic TMP and 2) avoids secondary purulent otorrhea.

While there is now more human data available that allows us to be confident about safety and efficacy of the clinical use of FGF-2, there are no studies conducted outside of the civilian population. In addition to conducting novel research in the United States, this study serves as a unique opportunity to advance current knowledge within the military population.

4. Study Objective

The primary outcome will be to determine the TMP closure efficacy of up to 3 treatments when compared to placebo.

4.1 Primary Objective

- To evaluate the efficacy of FGF-2 to repair chronic tympanic membrane perforations to complete closure as assessed by pre- and post-treatment photography when compared to placebo treated controls.

4.2 Secondary Objectives

- Determine the time to closure of tympanic membrane perforation for FGF-2 group and placebo group.
- Measure changes in pure-tone and speech discrimination scores in all study subjects.

- Determine mobility of tympanic membrane as measured by tympanometry in all study subjects.
- Observe salvage rate of FGF-2 treatment in subjects who failed placebo treatment.

5. Investigational Plan

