The sample size is calculated in 3:1 ratio to FGF-2 treatment group or placebo to provide more than 90% power to detect a clinical significant difference at a two-sided significance level of 0.05 using a Fisher's exact test. To allow for 5% dropouts, 45 patients of FGF-2 treatment group and 15 patients of placebo are required.

Data after discontinuations for any reason will not be imputed through the final schedule visit. This subject will be considered as not-improvement.

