13.1 Schedule of Assessments

Visit	0	1	2	3	4	5	6	7	Final Visit
Screening	Day 1 (± 7 days)	Day 22 (± 7 days)	Day 43 (± 7 days) As Needed	Day 64 ⁵ (± 7 days) As Needed	Day 85 ⁶ (± 7 days) As Needed	Day 106 ⁶ (± 7 days) As Needed	Day 127 ⁶ (± 7 days) As Needed		F/U ⁷ (± 7 days) As Needed
Informed Consent	X								
Inclusion/Exclusion Criteria	X								
Medical History Related to the Tympanic Membrane	X								
Otologic Exam	X								X
Vital Signs	X ²	X ²	X	X	X	X	X	X	X
Laboratory Evaluation /CBC, Basic Metabolic Panel, HbA1C/	X								X
Pregnancy Test ³	X								
Prior/Concomitant Medication	X	X	X	X	X	X	X	X	X
TM photography	X ^{1,2}	X ^{1,2}	X ¹	X ¹	X ¹	X ¹	X ¹	X ¹	X
Audiology		X ^{1,2}	X ¹	X ¹	X ¹	X ¹	X ¹	X ¹	X
Tympanometry									X
Study Drug Administration	X	X ⁴	X ⁴	X ⁴	X ⁴	X ⁴	X ⁴		
Review of Adverse Events	X	X	X	X	X	X	X	X	X

¹To be completed prior to administration of the investigational drug.

²This may be performed during the screening visit or during Day 1 Visit. Note: The first audiogram may have been performed within 60 days prior to subjects' enrollment.

³Women of child bearing potential will be required to have a negative pregnancy test. Either serum or urine tests are acceptable. Until study completion, adequate form of contraception must be ensured.

⁴Treatment given if the perforation has not closed at this visit.

⁵If the perforation has not closed at this visit, then the subject will be assigned to the other treatment group. The subject will then follow the same schedule of procedures as stated for Visit 5, Visit 6, Visit 7, and Final Visit.

⁶These visits will be completed by subjects that have been assigned to the other treatment arm and whose perforation still has not closed.

⁷The final study visit occurs 2 months (+/- 7 days) after the subject's last follow-up visit. The subject's last follow-up visit occurs when the subject's perforation is determined to be closed, or when the subject has completed the maximum number of study visits without perforation closure

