13.2 Efficacy Measurements

- Dose limiting toxicity/Optimal Biologic Dose is as defined in section 7.1
- TM closure is defined as complete closure of the tympanic membrane durable at both 21-days (± 7 days) and the test-of-cure Visit 5.
- TM Photographs will be obtained at every visit. A series containing pre- and post-treatment images will be digitally secured with Leica M320 high definition digital camera mounted with the Leica Microscope or with a 2.7 mm rigid Storz endoscope.
- Audiometric studies including pure tones (0.25, 0.5, 1, 2, 4, and 8 kHz) and speech discrimination scores will be recorded pretreatment and post treatment. A change of >10 dB across two frequencies or a change in speech discrimination of $> 20\%$ will be considered clinically significant on an NU-50 word list.
- Mobility of the tympanic membrane as measured by a Grayson Stadler GSI 37 Autotymp (Madison, WI) or equivalent tympanometer will be recorded when the TM appears healed otoscopically.

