17.5 Efficacy Analysis

Efficacy data from the Randomized Treatment phase will be evaluated by inspection, using student T-test, Cochran Mantel Hansel, or Kruskal-Wallis tests as appropriate; without conservation of alpha at 0.05. An interim analysis will be completed after approximately 50% of the study subjects (n=30) have been accrued.

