17.6 Secondary Efficacy Analysis

Secondary analysis of categorical data will be performed using Fisher's exact test for paired samples.

18. Safety Analysis

Safety will be assessed by evaluation of adverse events and clinical laboratory results and derived as data sets and frequency methods.

An independent Data and Safety Monitoring Board (DSMB) will follow the DSMB charter for this study. The DSMB Charter is commensurate with the level of risk of the study to its participants, complexity of the protocol, and ensure compliance with the principles and process of informed consent as well as privacy related regulations (e.g., HIPAA); and to monitor safety by recording (un-)expected adverse events (AEs) and their severity and attribution. The DSMB Charter includes a plan for periodic reviews of primary results and summary data as well as assessment of completeness and quality of collected data. All unexpected and/or serious adverse events as well as premature study withdrawals will be brought to the attention of the DSMB as early as possible in order for the DSMB to make judgments about participant safety, study modifications, and/or continuation. Not beyond the commencement of the proposed subsequent dose escalated cohorts, the DSMB will review study status to determine study progression. These will be based upon discussions between the research team and DSMB, and the decision of the board; no set stopping or escalating rules will be employed. The DSMB membership list is as follows:

[name], PhD - Chair and Research Monitor
MGH, Dana Farber/Harvard Cancer Center
Division of Hematology Oncology
[name]
[name]
Phone: [[name]]([contact])
Fax: [[name]]([contact])
Email: [contact]

[name], - Member
University of Minnesota
Department of Pediatrics
[name]
[name]
[name]
Phone: [[name]]([contact])
Fax: [[name]]([contact])
Email: [contact]

[name], Member (Statistician)
Director, Cooperative Studies Program Coordinating Center
Hines VA Hospital, CSPCC (151K)
[name],
[name]
Phone: [[contact]]([contact])
Fax: [[contact]]([contact])
[contact]

19. Research Monitor

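### Section 17.5 lists only unadjusted tests for continuous outcomes, so the hearing comparison would subtract the baseline audiogram without adjusting for it and lose some precision

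*Combined protocol and SAP*

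**What the plan says.** Section 4.2 sets the objective: "Measure changes in pure-tone and speech discrimination scores in all study subjects". Section 5.1 repeats it as a secondary outcome. Section 13.2 places audiometry among the efficacy measurements and says that pure tones and "speech discrimination scores will be recorded pretreatment and post treatment". The schedule in Section 13.1 puts audiograms at Visit 1 and at every later visit, before any study drug given that day. It adds: "The first audiogram may have been performed within 60 days prior to subjects' enrollment".

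Section 17.5 covers efficacy data from the Randomized Treatment phase, to be evaluated by inspection and "using student T-test, Cochran Mantel Hansel, or Kruskal-Wallis tests as appropriate; without conservation of alpha at 0.05". Section 17.6 adds only this: "Secondary analysis of categorical data will be performed using Fisher's exact test for paired samples". No section names ANCOVA, a regression model or a covariate, and no test is assigned to the hearing scores.

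The Synopsis derives 45 FGF-2 and 15 placebo subjects. The Synopsis and Section 10.2 also give a target of 75, which at 3:1 is 75/4, or about 19 on placebo.

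**The concern.** Of the tests in 17.5, only the t-test and Kruskal-Wallis suit an unstratified continuous outcome, and neither adjusts for baseline. Cochran-Mantel-Haenszel can stratify, but no stratum is named.

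Baseline is likely to matter. Section 2 says small perforations usually cause no hearing loss, while large ones can cost up to 30 dB. Entry criteria limit neither perforation size nor hearing loss, and randomization is not stratified on either. An ear with little loss has little to gain, so change will depend on where the ear started. Adjustment would use data the trial already collects. What is at stake is the width of the interval around the between-arm hearing difference, with a small placebo arm.

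**Working it through.** **Plan's own figure.** There is none for hearing. The sample size concerns closure only. The one hearing effect cited is a 13.6 dB mean improvement in closed ears in an uncontrolled series (Section 3.2), with no SD and no baseline-to-follow-up correlation r. Both SD and r are therefore assumptions below.

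**Step 1: equal SDs, one slope in both arms.** In units of the raw-score SD:

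- variance of a change score = 2(1 − r)
- residual variance after adjusting for baseline = 1 − r²
- ratio = (1 − r²) / [2(1 − r)] = (1 + r)/2

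The difference detectable with 80% power at two-sided 0.05 is (1.96 + 0.84) × SD × √(1/n₁ + 1/n₂). The square root is 0.298 for 15 v 45. Power is for an assumed true difference of 0.7 SD at 15 v 45 (noncentral t). Arrows run from change score to ANCOVA.

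| r | Variance ratio | Detectable, 15 v 45 (SD) | Detectable, 19 v 56 (SD) | Power at 0.7 SD |
|---|---|---|---|---|
| 0.5 | 0.75 | 0.835 → 0.723 | 0.744 → 0.644 | 64% → 76% |
| 0.7 | 0.85 | 0.647 → 0.597 | 0.576 → 0.531 | 85% → 90% |
| 0.9 | 0.95 | 0.374 → 0.364 | 0.333 → 0.324 | 99.9% → about 100% |

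The ratio does not involve n, so the proportional gain is the same with 15 or 19 on placebo. It is worth 1/0.75 = 1.33, 1/0.85 = 1.18 and 1/0.95 = 1.05 times the subjects. Simulation at 15 v 45 gave ratios of 0.77, 0.88 and 0.97, slightly above theory because a coefficient is estimated.

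**Step 2: chance imbalance.** A change score carries −(1 − r) times a baseline imbalance. With an assumed SD of 12 dB, a one-standard-error imbalance is 12 × 0.298 = 3.6 dB. The shift is then 1.8 dB at r = 0.5, 1.1 dB at r = 0.7 and 0.4 dB at r = 0.9, opposite in sign to the imbalance.

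**Step 3: unequal slopes.** If hearing gain comes mainly through closure, and closure differs by arm, the slope of follow-up on baseline will differ too. Take baseline SD 12, residual SD 6, and slopes of 1.0 (placebo, n = 15) and 0.4 (FGF-2, n = 45), all assumed.

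- Change score: the slopes of change are 0 and −0.6. Variance = 36/15 + (0.36 × 144 + 36)/45 = 2.400 + 1.952 = 4.352.
- Common-slope ANCOVA: the pooled slope is about 0.75 × 0.4 + 0.25 × 1.0 = 0.55, leaving 0.45 and −0.15 unexplained. Variance = (0.2025 × 144 + 36)/15 + (0.0225 × 144 + 36)/45 = 4.344 + 0.872 = 5.216, about 20% above the change score.
- Its model-based variance uses the pooled residual variance: (15 × 65.16 + 45 × 39.24)/60 = 45.72, times (1/15 + 1/45), giving 4.064. The nominal 1.96 cut-off acts like 1.96 × √(4.064/5.216) = 1.73, a type I error of about 8.4%.
- ANCOVA with a centred interaction: 36/15 + 36/45 + 0.6² × 144/60 = 2.400 + 0.800 + 0.864 = 4.064, a ratio to the change score of 0.93. The last term comes from estimating the baseline mean.

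Simulations agree. Common-slope variance was 22% and 24% higher in two runs, with type I error 8.3%. With slopes of 0.9/0.5 it was about equal to the change score, and with 0.8/0.4 it was 13% lower. The interaction model gave ratios of 0.99, 0.91 and 0.78 in these three cases, and 0.53 and 0.78 in two equal-slope cases.

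**The case against.** The strongest reply is that the plan commits to no between-arm test of hearing. The objective reads as descriptive, the list in 17.5 is generic, and Section 13.2 defines a clinically significant hearing change (more than 10 dB across two frequencies, or more than 20% in speech discrimination) that could be analysed as a category. This stands in part: a reader might infer that a t-test has been assigned to hearing, and the documents do not say so. But audiometry is listed as an efficacy measurement, 17.5 governs efficacy data from the randomized phase, and every option it offers for a continuous score is unadjusted.

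A reader might also infer that the baseline audiogram goes unused, or that a chance imbalance passes in full into the result. Neither is right. The objective is about change, which subtracts baseline, and only a fraction (1 − r) carries over, with reversed sign.

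The objection that ordinary ANCOVA need not help also stands, as Step 3 shows. It changes the model to be recommended and leaves the case for adjustment intact.

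Finally, the last Part A audiogram falls at a visit that depends on when closure occurs, so its timing may differ by arm. That is fair and needs a sensitivity analysis.

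**Conclusion.** The point holds as one about precision on a secondary outcome. The listed tests give up 25% of the variance at r = 0.5, 15% at r = 0.7 and 5% at r = 0.9, relative to a baseline-adjusted analysis with equal SDs and a common slope. With unequal slopes, the interaction model ranged from no material gain (0.99) to a clear one (0.78) in the cases examined. All of this rests on assumed r, SD and slopes, because the documents give none.

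Two stronger conclusions are not supported. The unadjusted comparison of change is not biased, since randomisation protects it, and nothing here touches the closure endpoint. Nor does the small placebo arm enlarge the proportional loss: it is the same at 15 or about 19, although the conflict between 60 and 75 subjects remains unresolved in the documents.

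**What to change.** In Section 17.5, state that pure-tone average (naming the frequencies averaged) and speech discrimination score will each be analysed as follows.

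- **Outcome:** the last Part A audiogram, taken at the visit where closure was found or at Visit 4 before any crossover treatment. Audiograms after crossover are excluded.
- **Model:** ANCOVA on arm, mean-centred baseline value and their interaction.
- **Standard errors:** robust, and allowing for the baseline mean being estimated. Routine software treats that mean as fixed, which in Step 3 would omit 0.864 of 4.064, or 21% of the variance.
- **Report:** the adjusted difference with its 95% confidence interval.
- **Sensitivity analyses:** the same model at Visit 2 (Day 22), the post-treatment visit in Part A not marked as needed only, which removes the dependence on time of closure; and a rank test on change.

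The cost is a few sentences of SAP wording, slightly more analysis work and one or two extra estimated coefficients. No visit or measurement is added.

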5.1 Overall Study Design and Plan Description

This study is a double blinded, placebo controlled phase II study evaluating the efficacy of FGF-2 for the treatment of chronic non-healing tympanic membrane perforations (TMP). The documentation of TM closure will be the main efficacy outcome measure. Pretreatment photographs will document the area of the TM perforation and allow measurement of surface areas of the TMP for comparison of pre- and post-treatment. The study will be divided into two phases, the Randomized Treatment phase (part A), and the Unblinded Crossover phase (part B). In part A of the study, subjects will be randomized 3:1 to receive FGF-2 or placebo treatment up to 3 treatments. Subjects that fail three study treatments will move on to part B of the study. Subjects who received placebo in part A and failed three placebo treatments will crossover to receive unblinded FGF-2 for up to 3 treatments. Subjects who received FGF-2 in part A and failed three experimental treatments will not have additional FGF-2 treatment, and will move on to study follow up.

The primary outcome for the study will be to determine the TMP closure efficacy of FGF-2 and placebo, with up to 3 treatments each. The OBD was determined to be 100 μ g of FGF-2 per 1 mL with an estimated dose of about 20 μ g in 0.2ml in prior studies by [name] (Kanemaru et al., 2011).

Secondary outcomes for the study include: (1) Determination of the time to closure of tympanic membrane perforation, (2) Measurement of changes in pure-tone and speech discrimination scores, (3) Determination mobility of tympanic membrane as measured by tympanometry, and (4) Observation of salvage rate of FGF-2 treatment in subjects who failed placebo treatment.

If both ears are affected by chronic perforation, only one ear will be initially enrolled in the study and receive treatment. The ear with the more significant symptoms will be the one enrolled in the study (i.e., greater conductive hearing loss). The non-study ear will not be enrolled or undergo additional treatments during the study period.

- 1) In an outpatient examination, the subject will be confirmed to have a tympanic membrane perforation by microscopic otoscopy and that no active infection and/or inflammation is present. Then a cotton ball soaked in 4% lidocaine jelly will be inserted with micro alligator forceps directly to the surface of the tympanic membrane under microscopic visualization.
- 2) After 15 minutes, the lidocaine infused cotton ball will be removed and the edge of the perforation roughened with a micropick to remove the epithelium circumferentially around the perforation edge.
- 3) A human fibroblast growth factor-2 (FGF-2) soaked pledget (approximately 20 µg in 0.2ml) of bioabsorbable gelatin sponge slightly larger than the tympanic membrane will then be placed against the lateral surface of the tympanic membrane to completely covered it. For the placebo group, only sterile water will be delivered by the pharmacy for saturation of the gelatin sponge.
- 4) The pledget will be secured in place with several drops of fibrin glue (Tisseel, McKesson Health Solutions, Auburndale, MA).
- 5) After the effects of the topical anesthetic have worn off, if any, the patient will be released with the following instructions:
 - a) Avoid violently sniffling or blowing the nose
 - b) Sneeze and cough naturally through the mouth without occluding the mouth with the hand.
 - c) Use cotton balls covered with petroleum jelly on the outer surface when washing the hair and bathing, to keep water out of the ear.
 - d) Avoid using a hearing aid in the treated ear.
 - e) Avoid flying, using elevators in tall buildings, and other situations involving substantial changes in air pressure.
 - f) Avoid swimming.
- 6) The subject will then come back at three weeks (+/- 7 days) for a follow- up appointment. The tympanic membrane will be examined to see if the perforation has closed and photographed in the same fashion as during the IMP or initial administration visit. Additional otologic tests will be performed during this follow up exam as well (See 13.1 Schedule of Assessments). If the tympanic

membrane has closed, then the participant will be seen again in approximately 2 months (+/- 7 days) for a final study visit.

However, if the perforation has not closed, then the FGF-2 or placebo application will be duplicated in the same fashion at this follow up visit. The subject will then be seen again at three weeks (+/- 7 days). The tympanic membrane will be assessed again. If the TMP is not healed, then a third application of the FGF-2 or placebo will be applied again at this visit. Additional otologic tests will be performed once again. If the TMP heals, then the subject will be seen again following this visit, or at approximately two months (+/- 7 days).

Once the subject completes Visit 1, Visit 2, and Visit 3, the subject will come back for Visit 4 (+/- 7 days). During this visit, the perforation will be examined again. If the perforation has not closed completely at this visit, then the blind on the subject's randomization status will be broken. If the subject was randomized to placebo, s/he will be crossed over to receive unblinded FGG-2 treatment. If the subject was randomized to FGF-2 treatment, s/he will receive no further study treatment and return in two months (+/- 7 days) for the final follow up visit.

If crossed-over to unblinded FGF-2 treatment, the subject may be given up to three additional treatments. The follow up visits will occur three weeks (+/- 7 days) and the same otologic procedures will be conducted as mentioned before (See Section 13.1, Schedule of Assessments). If the perforation is found to be closed during these visits or when the subject has completed the maximum number of study visits without perforation closure, then the subject will report in 2 months (+/- 7 days) for a final visit. The study will be completed for reporting purposes after all subjects have completed the 2 month (+/- 7 days) follow up final visit.

6. Discussion of Study Design

The investigator and the subject will be blinded to treatment assignment during the Randomized Treatment phase. Subjects whose perforations fail to close during the randomized treatment phase will crossover to the Unblinded Crossover Phase. During the crossover phase, only those subjects who failed placebo will receive unblinded FGF-2 treatment. The rationale for using a dose of 20 μ g in 0.2ml is based on the maximum effective dosages as reported in humans of TMR closure with FGF-2 (Kanemaru et al., 2011).

The subjects, physician, and other study staff members will remain blinded to the treatment arm during the randomized treatment phase as the pharmacy will oversee the randomization process. During the Randomized Treatment phase, the pharmacy will provide the appropriately blinded vial of either FGF-2 or placebo solution as needed upon the request from the physician. Only those subjects who fail the randomized treatment phase will crossover into the unblinded crossover phase. Documentation of the cross-over will be made in the Case Report Forms as well as in the randomization log managed centrally by the dispensing pharmacy.

7. Selection of Study Population

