1. SYNOPSIS

Protocol No.: 16-043H

TITLE: Fibroblast Growth Factor Regeneration of Tympanic Membrane Perforations
INVESTIGATIONAL PRODUCT: Human fibroblast growth factor-2 (FGF-2/bFGF/FGF-II) in a gelatin sponge, adhered by fibrin glue
INDICATION: Treatment of chronic non-healing tympanic membrane perforation
PHASE OF DEVELOPMENT: Phase 2
INVESTIGATIONAL SITES/LOCATIONS: Mass Eye and Ear Infirmary, Boston, Massachusetts
STUDY DESIGN: A Phase II randomized trial will be initiated to evaluate efficacy as the primary measureable outcome. Eligible and consented patients will be randomized in a 3:1 ratio to the optimal biologic dose (OBD) of FGF-2 or placebo (sterile water) during the Randomized Treatment Phase. Application of the study treatment may occur at the initial Screening Visit (pending all eligibility requirements can be confirmed) or at Visit 1 and may be repeated at each follow up visit as needed for a maximum of three treatments in the Randomized Treatment Phase. These follow up visits will occur three weeks (+/- 7 days) from the last treatment application. During these visits, the subject's tympanic membrane will be examined, photographed, and additional otologic tests will be performed. If the perforation is found to be closed during these visits, then the subject will report in 2 months (+/- 7 days) for a final study visit. If the subject's TMP has not closed after the third and final application of their assigned treatment group, then the blind on the subject's randomization status will be broken, and placebo patients will be crossed over to receive unblinded study drug. Again, the subject may be given up to three additional treatments in the unblinded crossover phase. The follow up visits will follow the same schedule, occurring three weeks (+/- 7 days) from the last treatment. The same otologic procedures will be performed as in the previous visits. All subjects will report for a final study visit 2 months (+/- 7 days) after their last follow up visit when the perforation is determined to be closed or when the subject has completed the maximum number of study visits without perforation closure. The study will be completed for reporting purposes after all subjects have completed the 2 month (+/- 7 days) follow up final visit.
NUMBER OF SUBJECTS (PLANNED): 75

DIAGNOSIS AND MAIN CRITERIA FOR INCLUSION:

Key inclusion criteria:

- Age 18 years and older
- Dry tympanic membrane perforation of greater than 3 months duration

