14.1 Visit 0, Screening

The following procedures will be performed:

- Administration of Informed Consent Form
- Review of inclusion and exclusion criteria
- Medical history of the Tympanic Membrane
- Otologic Exam
- Vital Signs
- Laboratory evaluation (hematology and chemistry): *CBC, Basic Metabolic Panel Test, HbA1c*
- Pregnancy Test if applicable
- Review of Prior/ Concomitant medication(s)
- Optional: Study drug administration (if all eligibility requirements can be confirmed at this visit)
- Optional: TM photography
- Optional: Audiogram

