14.4 Visit 4, 64 days after the first treatment (± 7 Days)

The following procedures will be performed:

- Study Drug administration- *If the TMP is not completely closed, then the blind on the subject's randomization status will be broken. Placebo subjects will be crossed over to FGF-2 treatment arm at this visit.*
- Vital Signs
- Review of Prior/ Concomitant medication(s)
- TM photography
- Audiogram
- Assessment of Possible Adverse events

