14.6 Visit 6, 106 days after first treatment (± 7 Days)

This is a follow up visit for all subjects who were crossed over to the other treatment group at Visit 4. The following procedures will be performed:

- Study Drug administration- *if the TMP is not completely closed*
- Vital Signs
- Review of Prior/ Concomitant medication(s)
- TM photography
- Audiogram
- Assessment of Possible Adverse events

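### Placebo failures receive their first FGF-2 at Visit 4 on a pregnancy test taken at Visit 0, nominally 63 days earlier, with no repeat test scheduled before that dose

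*Combined protocol and SAP*

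**What the plan says.** Section 5.1, step 3, defines the control: "For the placebo group, only sterile water will be delivered by the pharmacy for saturation of the gelatin sponge". A placebo subject therefore has no FGF-2 exposure during the Randomized Treatment Phase.

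For a placebo subject whose perforation has not closed by Visit 4, section 5.1 states: "If the subject was randomized to placebo, s/he will be crossed over to receive unblinded FGG-2 treatment" (the drug name is a typing slip for FGF-2). Section 14.4 agrees: "Placebo subjects will be crossed over to FGF-2 treatment arm at this visit". Up to three FGF-2 applications may follow, at Visits 4, 5 and 6.

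Section 14.1 lists "Pregnancy Test if applicable" at Visit 0. The lists in 14.2 to 14.8 do not include the test, and its row in the 13.1 schedule carries a single mark. Footnote 3 to that schedule says of the method: "Either serum or urine tests are acceptable".

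Several other provisions bear on the point:
- Sections 7.1 (item 3) and 13.1 (footnote 3) require contraception for the whole study.
- Section 7.4 names pregnancy among the potential reasons for removal from treatment.
- Section 7.3 withholds further treatment after three failed applications if there are ear complications.
- Section 5.1, step 1, requires confirmation that there is no active infection or inflammation before an application.

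**The concern.** The protocol does not rely on contraception alone at entry. It also asks for a negative test, and section 10.3 allows dosing only once eligibility assessments are complete. In the FGF-2 arm that test precedes the first active dose. In the placebo arm it precedes a sterile-water dose, and the first active dose comes about nine weeks later. Section 14.2 repeats the eligibility review at Visit 1. Section 14.4, which is the first-dose visit for a crossover subject, lists neither that review nor a test.

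What is at stake is a woman's first exposure to an investigational growth factor during a pregnancy that nobody has looked for since screening. Section 2.3 gives FGFs a substantial role in development, section 2.4 lists embryonic tissues among those expressing FGF-2, and section 13.4 plans no pharmacokinetics. None of this shows harm from about 20 µg applied topically. It does make a current negative test a reasonable precondition.

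**Working it through.** **Inputs.** Treatment interval 21 ± 7 days, timed from the previous application (Synopsis: "These follow up visits will occur three weeks (+/- 7 days) from the last treatment application"; also 13.6). Day 1, Day 64 and Day 106, each ± 7, for Visits 1, 4 and 6 (13.1). First dose possible at Visit 0 itself (14.1), so the shortest time from test to first dose is 0 days. No upper limit on the Visit 0 to Visit 1 gap is stated.

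**Reproducing the schedule.** Visit day = 1 + 21 × (visit number − 1). Visit 4: 1 + 63 = 64. Visit 6: 1 + 105 = 106. Both match 13.1.

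**Age of the pregnancy test at the first crossover dose (Visit 4), before adding any Visit 0 to Visit 1 gap:**
- Nominal: 3 × 21 = 63 days.
- Chained intervals: 3 × 14 = 42 to 3 × 28 = 84 days.
- Fixed calendar with Day 1 held fixed: (64 − 7) − 1 = 56 to (64 + 7) − 1 = 70 days.
- Fixed calendar with the Day 1 window as well (Day −6 to Day 8, counting straight through zero): 57 − 8 = 49 to 71 − (−6) = 77 days.
- Section 14.4 heading, "Visit 4, 64 days after the first treatment", ± 7: 57 to 71 days.

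The minimum is 42 days or more on every reading.

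**Third crossover dose (Visit 6).** Nominal 5 × 21 = 105 days; chained 5 × 14 = 70 to 5 × 28 = 140 days. The section 14.6 heading, "Visit 6, 106 days after first treatment", ± 7, gives 99 to 113 days.

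**Nominal test age at FGF-2 doses 1, 2 and 3 (plus the same Visit 0 to Visit 1 gap in the first two rows):**

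| Group | Dose 1 | Dose 2 | Dose 3 |
|---|---|---|---|
| FGF-2 arm | 0 | 21 | 42 |
| Crossover, as written | 63 | 84 | 105 |
| Crossover with a Visit 4 test | 0 | 21 | 42 |

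**How many women (assumption-based).** Placebo subjects: 60/4 = 15 (target in 17.1) or 75/4 = 18.75 (planned number in the Synopsis). The documents give no planning value for placebo closure, so a range is used:
- 10% closure (1 of 10 human controls at three weeks, section 3.2): 15 × 0.9 = 13.5 to 18.75 × 0.9 = 16.9 crossovers.
- 10% at each of three applications: 0.9³ = 0.729, giving 15 × 0.729 = 10.9 to 18.75 × 0.729 = 13.7.
- 41% closure (chinchilla controls, section 3.1): 15 × 0.59 = 8.9 to 18.75 × 0.59 = 11.1.

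That is about 9 to 17 crossovers before dropouts and 7.3 exclusions. If 10% to 30% are women of child-bearing potential (assumed; no share is given), 9 × 0.10 = 0.9 to 17 × 0.30 = 5.1, or about 1 to 5 tests. The documents give no pregnancy rate, so the expected number of exposed pregnancies cannot be computed.

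**The case against.** The best opposing argument is that first exposure is not a special moment. A woman who conceives after Visit 0 is exposed just as much by a second or third FGF-2 dose in Part A, and those doses have no re-test either. The FGF-2 arm is larger (60 × 3/4 = 45 to 75 × 3/4 = about 56 subjects), and by its third dose the test is nominally 42 days old. The documents give no cut-off that makes 42 days acceptable and 63 not. This stands as a limit on weight: lack of re-testing is not unique to crossover. What is specific to crossover is that even the first active dose has no test tied to it, and that gap can be closed at an existing visit.

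Existing controls also count. Contraception is compulsory throughout, pregnancy can lead to removal, and staff ask open-ended questions about adverse events at every visit (15.1). Consent pages are not available, so any reporting instruction there cannot be seen. These controls lower the risk, but prevention is not detection, and removal acts only on a pregnancy already known.

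A reader might infer that the crossover dose follows automatically from an open perforation and a placebo assignment. The documents do not support that: section 7.3 withholds treatment for ear complications, and 5.1, step 1, requires an ear free of active infection and inflammation. A reader might also infer that fetal harm is likely, or that the efficacy result is compromised. The documents contain no reproductive-toxicity or absorption data, so harm is neither shown nor excluded. Crossover begins only after the randomized outcome at Visit 4 has been assessed.

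**Conclusion.** The point holds as a minor safety gap with a cheap remedy. As written, a placebo subject may receive her first FGF-2 on a pregnancy test nominally 63 days old, and no condition on that dose would reveal a pregnancy she does not know about. The timing follows from the visit schedule alone. The choice between chained and fixed-calendar windows changes the range but not the conclusion. The number of women concerned is small and rests on assumed placebo closure and an assumed share of child-bearing potential. The Part A comparison needs no change.

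**What to change.** Add a pregnancy test at Visit 4 in three places: section 5.1 (crossover paragraph), the pregnancy-test row of 13.1, and the 14.4 list. Suggested text:

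> After the blind is broken and before the first crossover FGF-2 application, women of child-bearing potential must have a negative urine or serum pregnancy test. A subject with a positive test receives no FGF-2 and proceeds to the 2-month final visit.

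Doing this after unblinding limits testing to subjects about to receive FGF-2. It brings the nominal test age at the three crossover doses to 0, 21 and 42 days, matching the FGF-2 arm apart from that arm's Visit 0 to Visit 1 gap.

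The cost is the protocol wording, a few urine tests (about 1 to 5 under the assumptions above) at a visit that already takes place, using a method the protocol already accepts, and possibly one fewer subject in the salvage evaluation.
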